	
Safety Analyses: Statistical methods for the safety analyses will be descriptive in nature. Safety data, including AEs, clinical laboratory data, vital signs, ECG parameters, and PEs. All appropriate AEs will be graded using the DMID toxicity scale (March 2014). Change from baseline will be included in summary tables for laboratory parameters. All laboratory data will be included in the data listings and all test values outside the normal range will be flagged.
 
Pharmacokinetic Analyses: Plasma PK parameters for each dose level in the SAD part of the study will be calculated from the concentrations of B-OT and OT measured in pre-dose and post-dose plasma samples. For each dose level, descriptive statistics will be presented. Figures will be created to display mean and individual subject B-OT and OT concentration versus time. Plasma PK parameters for each dose level in the MAD part of the study will be calculated from the concentrations of OT and possible derivate metabolites. Figures will be created to display mean and individual subject OT concentration versus time.
 
Interim Analyses: No formal interim analyses are planned for this study. Data from SAD cohorts were frozen and analyzed prior to conducting the second MAD part of the study.

--	--

TABLE 1: VISIT AND ASSESSMENT SCHEDULE OF THE SINGLE ASCENDING DOSE PART

Visit	Screening (Days -28 to -2)	Day -1	Day 1 (T=0)	Day 2 (24 hr) +/- 30min	Day 3 (48 hr) +/-1hr	Day 4 (72 hr) +/-1hr	Day 8 (EOS) (168 hr) +/-2hr	
Informed consent	x							
Demography	x							
I/E; Medical history	x	x						
Physical examination-PE ¹	x	x	x ²	x		x	x	¹ : a complete PE will be performed at Screening and/or Check-in and EOS; on all other days, a limited PE will target any change from the previous status, or any body system deemed pertinent to that subject by the PI (or designee) ² : at 4 hr post-dose
Vital signs ³	x	x	x	x	x	x	x	³ : vital signs include pulse rate, respiratory rate, blood pressure and body temperature; on Day1, VS should be taken pre-dose and at 2,4, 8 and 12 hr post-dose
Laboratory assessment (hematology, biochemistry)	x	x ⁴		x		x	x	⁴ : Results for safety blood samples must be available and reviewed before drug is administered
Urine analysis	x	x		x	x	x	x	
ECG	x		x ⁵	x			x	⁵ : the baseline ECG should be conducted prior to dosing on day 1
SARS CoV antigen	x						x	
SARS CoV PCR		x				x		

Study Protocol

Study number: BV-01-101

Version No. : 3.0

Date: 13 Jul 2022

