Urine analysis	x	x		x			x			x	x	x	
ECG	x		x ⁵	x		x			x			x	⁵ : the baseline ECG should be conducted prior to dosing on Day 1, and subsequent ECGs should be taken at pre-dose on the rest of the dosing days and at time of visit on ambulatory visit days
SARS CoV antigen	x	x										x	

CONFIDENTIAL

Study Protocol

Study number: BV-01-101

Version No. : 3.0

Date: 13 Jul 2022

Visit	Screening (Days -28 to -2)	Day -1	Day 1	Day 2	Day 3	Day 4	Day 5	Day 6	Day 7	Day 8	Day 11	Day 14 (EOS)	
Viral screening (HIV, Hepatitis)	x												
Drug screening	x	x										x	
Breath alcohol test	x	x										x	
Weight/height (BMI)	x	x ⁶				x ⁶				x ⁶	x ⁶	x ⁶	⁶ : only weight
Plasma PK sample collection			x ⁷	x ⁸	x ⁸	x ⁸	x ⁸	x ⁸	x ⁷	x ⁸	x ⁸	x ⁸	⁷ : PK samples should be collected pre-dose and at 0.25, 0.5, 0.75, 1, 1.5, 2, 4, 8, 12 hr, on Day 1 and Day 7. Depending on ongoing PK data review, timepoints may be modified or removed. ⁸ : PK samples should be collected pre-dose on Day 2, 3, 4, 5 and 6 and 24hr +/- 30 min (Day 8), 96hr +/- 4hr (Day 11) and 168hr +/- 4hr (Day 14) after last dosing of Day 7.
PD ⁹			x ⁹	x		x ⁹	x		x ⁹	x			⁹ : PD blood sample should be taken pre-dose and at 1, 2, 4, 8, and 12 hr after dosing on Day 1, Day 4 and Day 7. One sample per day should be taken on Day 2 and Day 5 pre-dose, corresponding to 24 h after previous day dosing. One sample should be taken 24 h after previous day dosing on Day 8.
Adverse Events	x ¹⁰	x ¹⁰	x ¹⁰	x	x	x	x	x	x	x	x	x	¹⁰ : Adverse events occurring prior to study drug administration should be recorded as medical history unless the event is directly related to study specific procedure
Prior and/or Concomitant medications	x	x	x	x	x	x	x	x	x	x	x	x	

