The SAD part of the study showed good tolerability and there were no side effects detected after once-daily administration of B-OT at an escalating dose ranging from 0.5 mg to 5 mg.

No B-OT was detected at any dose level in the plasma of the healthy volunteers.

At the maximum dose of 5 mg, the maximum concentration of OT in human plasma was 15.45 ± 3.76 ng/ml. The time to reach the maximum concentration ranged at the different dose between 1.67 ± 0.29 and 2.50 ± 1.18 hours.

Following single administrations of B-OT, the exposure to OT in terms of C_{max} and AUC_{0-t} increased with ascending doses from 0.5 to 5 mg in a slightly over proportional manner.

Further details can be found in the IB.

Study Rationale

This is a FIH clinical study and as such is conducted primarily to obtain information on safety, PK and PD properties of the tested compound. The scientific rationale of the study is based on the information that RNA viruses such as SARS-CoV-2 bring their own RNA polymerase into the cell. However, after infecting the cell and releasing their viral RNA, they depend on precursors necessary for replication of their viral RNA. The virus is dependent on ribose-5-phosphate (R5P) from the host cell as an essential building block for their replication.

The central switch for the regulation of cell cycle and cell proliferation as well as for the sufficient supply of R5P building blocks is provided by transketolase-like 1 (TKTL1) [Li et al., 2019], which therefore represents a good target for antiviral therapy.

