The safety and tolerability of B-OT were assessed through a series of non-clinical toxicity studies, which included safety pharmacology investigations. The safety pharmacology investigations in rats (i.e., Irwin study) showed effects in female animals (1000 mg/kg/day) which were in a bad condition at the moment of the investigations. In the dog cardiovascular investigations, no effects on ECG by conventional ECG measurement. In a jacketed telemetry measurement, increases in heart rate were observed, at a supra-NOAEL dose level. In the same study no effect on respiratory functions were recorded.

Two-cycle (i.e., 1-week treatment followed by a 1-week treatment free period per cycle) repeat dose toxicity studies with B-OT were performed in rats and dogs. Female rats at the highest tested dose level (1000 mg/kg/day) were all prematurely euthanized on Day 7 of the study because of moribund condition. Other effects noted in the rats were lower body weight, transient hematological effects and some effects on cholesterol and triglyceride levels. In dogs one female animal was found dead on Day 5 in the second treatment cycle. Effects in surviving

animals were lower body weight and food consumption, which were partially reversed after a 1-week treatment-free period, as well as some transient changes in clinical pathology parameters. Furthermore, some non-adverse histopathological effects in thymus tissue were found. The No Observed Adverse Effect Level (NOAEL) for the rat study was set at 1000 mg/kg/day (males) and 300 mg/kg/day (females), and the NOAEL for the dog study was set at 0.15 mg/kg/day for both sexes.

Dosing is based on $\text{NOAEL} \times \text{HED} \times 1/10$ (No Observed Adverse Effect Level \times Human Equivalent Dose [dog/human] \times Safety Factor). As NOAEL was established in dog after a 7-day treatment and B-OT has already been used in compassionate use at a minimum daily dose of 3 mg for 7 days in 5 Covid-19 patients and 5 late-stage prostate cancer patients without any safety issue, only 3 subjects in the SAD part will receive the two first lowest doses.

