11 STUDY ENDPOINTS

11.1 Primary endpoints

The outcome measures for the safety endpoints of the study will be safety laboratory assessments, physical examination (PE), electrocardiograms (ECGs), vital signs, adverse events (AEs) and serious adverse events (SAEs).

The safety variables will mainly be addressed by the adverse events (AEs) data as determined by clinical or biochemical/ hematologic investigations.

The safety variables will be tabulated for all study participants. AE data will be processed in the statistical analysis after coding according to MedDRA dictionary. AEs will be presented in summary tables. These tables will show the number of subjects per group presenting an AE and the incidence of its occurrence. AEs will be grouped by system organ class and stratified by severity and by relation to study treatment.

Adverse events which will be summarized and will be categorized in subsets of all treatment-emergent AEs, and of all treatment-related AEs.

Clinical laboratory and vital signs will be summarized by change from baseline.

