14.8.3 ECG

At each time point, absolute values and change from baseline of ECG numeric variables will be summarized with n, mean, SD, SEM, median, Min, and Max values. The number of available observations and out-of-range values (absolute and in percentage) will be presented. Values outside the investigator's normal range will be flagged in the listing. 'H' and 'L', denoting values above or below the investigator reference range (when present), will flag out-of-range results.

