#### Safety Data and Adverse events

Table II.14.3.1 Overall Incidence of Treatment Emergent Adverse Events

Table II.14.3.2 Treatment Emergent Adverse Events, by SOC and PT

Table II.14.3.3 Related Treatment Emergent Adverse Events, by SOC and PT

Table II.14.3.4 Treatment Emergent Serious Adverse Events, by SOC and PT

Table II.14.3.5 Summary of Hematology Parameters - Actual Values and Change from Baseline

Table II.14.3.6 Summary of Biochemistry Parameters - Actual Values and Change from Baseline

Table II.14.3.7 Summary of Urinalysis Parameters

Table II.14.3.81 Summary of Vital Signs: Actual Values and Change from Baseline

Table II.14.3.12 Overall ECG Assessment

Table II.14.3.13 Concomitant Therapy by ATC code (if appropriate)

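### No ECG in either part is scheduled near the oxythiamine peak, so a peak-concentration effect on PR, QRS or QTcF cannot be seen; the SAP also lists no numeric ECG table

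*Protocol*

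**What the plan says.** **Endpoint.** Protocol 11.1 names ECG among the primary safety measures.

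**SAD schedule.** In Protocol Table 1, footnote 5 states that "the baseline ECG should be conducted prior to dosing on day 1". The later ECGs are on Day 2 (24 h) and Day 8 (168 h). Section 12.1 agrees.

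**MAD schedule.** In Protocol Table 2, ECGs are marked on Days 1, 2, 4, 7 and 14. Footnote 5 says that "subsequent ECGs should be taken at pre-dose on the rest of the dosing days". Section 12.2 repeats pre-dose for Days 1, 2, 4 and 7. Day 8 has no ECG.

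**Peak time.** Section 6.1 reports from the completed SAD part: "The time to reach the maximum concentration ranged at the different dose between 1.67 ± 0.29 and 2.50 ± 1.18 hours".

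**Nonclinical background.** Section 8.3 reports for dogs: "In a jacketed telemetry measurement, increases in heart rate were observed, at a supra-NOAEL dose level". The sentence before it reports no effects on conventional dog ECG.

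**Analysis.** Protocol 14.8.3 says that at each time point "absolute values and change from baseline of ECG numeric variables will be summarized", with counts of out-of-range values. The only ECG summary table in the SAP's MAD list is "Table II.14.3.12 Overall ECG Assessment"; the SAD list has the matching Table I.14.3.9.

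**The concern.** In the MAD part, every ECG taken during treatment is a trough recording, and in the SAD part the first ECG after dosing is a day later. If OT or a related metabolite changed conduction or repolarisation in step with plasma concentration, the effect would be largest a few hours after dosing, when no ECG is planned. A clean set of ECGs would then say little about PR, QRS or QTcF at peak. The observed tmax was already known when protocol version 3.0 set the MAD schedule.

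The reporting adds to this. The protocol asks for numeric ECG summaries, but the SAP's output list names no table for them, so small shifts in an interval could go untabulated in a study with 6 subjects per MAD cohort.

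**Working it through.** No power or alpha figure is involved (Protocol 14.3: not applicable), so the check is a count of ECG times, an illustration of exposure, and a comparison of the two documents.

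**Step 1: the peak window.** Inputs are the tmax values in Protocol 6.1. The lowest mean less its SD is 1.67 − 0.29 = 1.38 h. The highest mean plus its SD is 2.50 + 1.18 = 3.68 h.

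**Step 2: scheduled ECGs after the first dose** (Protocol Tables 1 and 2)

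| Part | ECG | Nominal time since last dose | Within 1.38–3.68 h? |
|---|---|---|---|
| SAD | Day 2 | 24 h | No |
| SAD | Day 8 | 168 h | No |
| MAD | Day 2 pre-dose | 24 h | No |
| MAD | Day 4 pre-dose | 24 h | No |
| MAD | Day 7 pre-dose | 24 h (after the Day 6 dose) | No |
| MAD | Day 14 | 168 h | No |

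The count is 0 of 2 in the SAD part and 0 of 4 in the MAD part. The nearest ECG comes 24 − 2.50 = 21.5 h to 24 − 1.67 = 22.3 h after mean tmax. After the Day 7 dose the next ECG is at 168 h.

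**Step 3: exposure at the 24 h ECG.** The documents give no OT half-life, so this is an illustration. Assuming a single first-order decline from the peak, C24/Cmax = 0.5^((24 − tmax)/t½). The two ends of each range use tmax = 1.67 and 2.50 h.

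| Assumed t½ | C24 as % of Cmax |
|---|---|
| 4 h | 2.1 to 2.4 |
| 6 h | 7.6 to 8.3 |
| 12 h | 27.5 to 28.9 |
| 24 h | 52.5 to 53.7 |
| 48 h | 72.4 to 73.3 |

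**Step 4: what else is measured near the peak.** SAD vital signs, which include pulse, are taken at 2, 4, 8 and 12 h on Day 1 (Table 1, footnote 3). MAD vital signs are taken at 4 h post-dose on Days 2, 5 and 7 (Table 2, footnote 3). These give heart rate but no PR, QRS or QTcF.

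**Step 5: protocol and SAP side by side**

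- Protocol 12.3.4 has the device calculate heart rate, PR, QRS, QT and QTcF, so the numeric data exist.
- Protocol 14.8.3 requires their values, change from baseline and out-of-range counts at each time point.
- SAP 2.1 counts ECG parameters among the safety assessments. SAP 5 promises descriptive statistics for quantitative variables, and SAP 6.2 promises change from baseline for continuous safety measures. Together these imply numeric ECG summaries.
- SAP 11 mentions the 12-lead ECG in its opening lines. Its subsections then cover adverse events, laboratory, vital signs and concomitant therapy, with none for ECG.
- In the output lists, hematology, biochemistry and vital signs each have a table of actual values and change from baseline. ECG has only the overall assessment. The ECG listing does not mention change from baseline, while the laboratory and vital-signs listings do.

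**The case against.** The other side has several fair points.

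- **The SAP still covers numeric ECG in general terms.** A reader might infer that the SAP drops the numeric analysis and will report ECG only as a category. The documents do not support that: SAP 2.1, 5 and 6.2 imply numeric summaries, and SAP 1 commits all analyses to protocol version 3.0. What stands is that no table is listed to deliver them.
- **Heart rate was measured at the peak.** A reader might also infer that nothing is known about heart rate near Cmax. SAD pulse at 2 h, up to 5 mg (the top planned MAD dose), contradicts this. The gap is PR, QRS and QTcF.
- **The dog finding is not an ECG-interval signal.** It is a heart-rate increase above the NOAEL, alongside no effect on conventional ECG. It does not show a conduction or repolarisation risk.
- **Trough recordings have value.** The protocol describes OT as an irreversible enzyme inhibitor (6.1), so an effect need not follow plasma concentration, and a delayed or cumulative effect could appear at trough. This stands, and it argues for keeping late pre-dose ECGs.
- **Timing can be adapted.** Section 8.6.4 allows changes between cohorts and 12.3 allows extra procedures at any time. Both are discretionary; neither schedules an ECG near the peak.
- **The study is exploratory and small.** True, but ECG is a named primary measure, and re-timing one recording needs no larger sample.

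**Conclusion.** The timing point holds in full and does not depend on half-life: no scheduled ECG in either part lies within 20 h after mean OT tmax, and the last MAD dose has none for 168 h. The ECG part of the primary safety endpoint therefore cannot show a peak-concentration effect on PR, QRS or QTcF.

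It would go too far to say that the planned ECGs see only a small share of peak exposure. The range of about 2% to 73% of Cmax rests on assumed half-lives of 4 to 48 h and a single first-order decline, and the documents cannot narrow it. Using the single-dose tmax for the MAD part is also an assumption, but the gap is too wide for a modest shift to matter.

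The SAP point is a narrower one of reconciliation: a numeric summary that Protocol 14.8.3 requires, and that the SAP's general rules imply, is missing from the SAP's output list for both parts. Both points are worth correcting.

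**What to change.** **Protocol.** In Table 2 footnote 5 and section 12.2.9, move the Day 7 MAD ECG from pre-dose to about 2 h post-dose, beside the 2 h PK and PD draw already scheduled. Day 7 is the better choice because Day 4 has a PD draw at 2 h but no PK draw. Keep the pre-dose ECGs on Day 1 as baseline and on Days 2 and 4 as trough recordings. State that the 5-minute supine rest in 12.3.4 is an exception to section 9.5 item 8, which keeps subjects seated or ambulatory for 4 h after dosing; the supine SAD vital signs at 2 h already needed the same exception. The SAD part is complete, so its schedule cannot change.

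**Cost.** The number of ECGs is unchanged and subjects are confined that day. The downside is one fewer trough ECG, and the Day 7 pre-dose check under 12.3 would no longer include an ECG. Adding the 2 h ECG instead of moving it avoids that loss, at one extra recording per subject (24 across the 4 × 6 MAD subjects).

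**SAP.** Add an ECG subsection to section 11 and, for each part, a table of heart rate, PR, QRS, QT and QTcF: actual values, change from baseline and out-of-range counts, to match Protocol 14.8.3. This uses data already collected and costs one table per part.

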6 INTRODUCTION AND RATIONALE

6.1 Introduction

Benfo-oxythiamine (B-OT) is a novel inhibitory thiamine analogue that acts as a prodrug and releases oxythiamine in the human body. B-OT is a previously unknown dosage form of oxythiamine which, like the drug benfotiamine (trade name Milgamma), has a lipophilic side group, the benfo group. Its introduction into a molecule improves its cell permeability and can thus ensure better bioavailability [Bitsch et al.,1991].

The active substance in the investigational medicinal product capsules is the small molecule benfo-oxythiamine (B-OT). B-OT represents a novel inhibitory thiamine (vitamin B1) analog and prodrug which is converted in the human body into oxythiamine. Oxythiamine is a thiamine antagonist and inhibits transketolase, the enzyme that controls the nonoxidative branch of the pentose phosphate pathway (PPP). Via the intermediate ribose-5-phosphate, the PPP supplies ribonucleotides for SARS CoV 2 replication. Therefore, it is hypothesized that the inhibition of transketolase by B-OT will reduce the capacity for viral replication.

SARS-CoV-2 (severe acute respiratory syndrome coronavirus type 2) is a new coronavirus that was identified as the cause of COVID-19 in early 2020. In March 2020, the WHO declared the outbreak of SARS-CoV-2 infections a pandemic.

The course of a SARS-CoV-2-infection varies in symptoms and severity, from asymptomatic infections to severe pneumonia with lung failure, multiple organ failure and death. The most common symptoms include cough, fever, rhinitis, sore throat, gastrointestinal symptoms and neurologically associated symptoms such as the loss of the sense of smell or taste [Lechien JR, et al. 2019; Yan CH, et al. 2020; Tong Jy, et al. 2020]. Other neurologically associated symptoms include headache, dizziness, cognitive impairment, and fatigue, which can also occur after mild courses and can manifest long after the acute SARS-CoV-2 infection has already resolved [Schenk M 2020; Li YC, et al. 2020; Whittaker A, et al. 2020; Kennedy M, et al. 2020; Hampshire A, et al. 2020]. This can significantly compromise the long-term health and quality of life of patients.

Some SARS-CoV-2 patients develop COVID-19 disease, which is associated with lung damage, oxygen deficiency and respiratory distress. Pneumonia may develop, usually in the second week of illness, and may progress to ARDS (Acute Respiratory Distress Syndrome), requiring ventilation and intensive care and possibly oxygenation of the blood outside the body (ECMO) [Yang X, et al. 2020; Graselli G, et al. 2020; Rieg S, et al. 2020]. Moreover, COVID-19 can also manifest in other organ systems. The sites of manifestation depend, among others, on the density of ACE-2 receptors (entry portal of the virus into the cell) in the tissues. High ACE-2 density exists in the respiratory tract, as well as in the intestine, vascular cells, kidney, heart muscle and other organs.

Severe courses of SARS-CoV-2 infection are often associated with an excessive reaction of the immune system („cytokine storm“). The virus can invade lung epithelial cells and alveolar macrophages and induce production of viral nucleic acid by use of cellular enzymes. The virus infection causes a metabolic switch from mitochondrial energy release (OxPhos) to a glucose-based energy release (aerobic glycolysis). This metabolic switch stimulates the release of large amounts of cytokines, as well as activates macrophages, dendritic cells, and others, leading to multisystem organ failure and death. Inhibition of glucose metabolism by 2-deoxy-glucose (2DG) inhibits virus replication in infected cells confirming the critical role of glucose metabolism.

Drugs that inhibit immune system activity, such as dexamethasone, show positive effects on severe disease courses. Nevertheless, a high proportion of patients undergoing a severe course of SARS-CoV-2 infection die. According to the study of critical illness courses during the first COVID-19 epidemic, 47% of cases treated with intensive care died [Schilling J, et al. 2020].

Containment of the SARS-CoV-2 pandemic is massively complicated by the fact that, firstly, SARS-CoV-2 infections can also proceed asymptomatic, and therefore apparently healthy people infect others, thus facilitating the further expansion of the virus. Secondly, new and faster-spreading viral mutations have now emerged and can lead to a sudden increase in the number of cases. This poses the risk of overloading the healthcare system and hospitals – as is currently the case, for example, in the UK, Portugal and Brazil.

B-OT is a novel drug candidate in development as a therapy for COVID-19. It is intended that patients diagnosed with COVID-19, i.e., people with disease symptoms and confirmed diagnosis of SARS-CoV-2 viral infection, will be treated with B-OT capsules. It is anticipated that B-OT will actively interfere with viral replication and lead to fast recovery and cure of COVID-19. In consequence, the risk for disease aggravation and hospitalization will be reduced, as well as long-term fatigue and similar lingering symptoms experienced by some COVID-19 patients.

The clinical development program will investigate the potential of B-OT to shorten the time to recovery from COVID-19 and to prevent hospitalization. It will further generate data on safety and potential adverse reactions.

In the FIH clinical trial, safety will be assessed through the incidence and severity of adverse events at each of the dose levels tested. Furthermore, for clinical and laboratory parameters change from baseline will be assessed, to assess the overall safety profile and tolerability of B-OT.

In subsequent clinical investigations – to be conducted in patients with SARS-CoV-2 infection and COVID-19 – the above evaluations will be complemented with clinical efficacy assessments, such as, but not limited to, overall response, prevention of progression, and reduction in the need for oxygen supplementation.

To support the clinical development of B-OT, several non-clinical safety studies have been performed using the oral route of administration, according to the requirements of the M3(R2) ICH guideline (Nonclinical safety studies for the conduct of human clinical trials) [M3 (R2) ICH Guideline S9, EMA 2009]. All pivotal toxicology and toxicokinetic (TK) studies reported in this Investigator's Brochure (IB) were conducted in accordance with the Good Laboratory Practice (GLP) principles. Pilot, exploratory, and ADME studies were not conducted under strict GLP procedures but were conducted using appropriate protocols and documentation to ensure data integrity. In the in vivo studies as performed, B-OT was administered as a solution in drinking water, by oral (gavage) administration.

The clinical development of B-OT has started. The single ascending dose (SAD) part of this study assessing the safety, tolerability, and pharmacokinetics of B-OT in healthy volunteers has been completed and the multiple ascending part (MAD) will start as soon as the amendment of this protocol has been approved.

The SAD part of the study showed good tolerability and there were no side effects detected after once-daily administration of B-OT at an escalating dose ranging from 0.5 mg to 5 mg.

No B-OT was detected at any dose level in the plasma of the healthy volunteers.

At the maximum dose of 5 mg, the maximum concentration of OT in human plasma was 15.45 ± 3.76 ng/ml. The time to reach the maximum concentration ranged at the different dose between 1.67 ± 0.29 and 2.50 ± 1.18 hours.

Following single administrations of B-OT, the exposure to OT in terms of C_{max} and AUC_{0-t} increased with ascending doses from 0.5 to 5 mg in a slightly over proportional manner.

Further details can be found in the IB.

Study Rationale

This is a FIH clinical study and as such is conducted primarily to obtain information on safety, PK and PD properties of the tested compound. The scientific rationale of the study is based on the information that RNA viruses such as SARS-CoV-2 bring their own RNA polymerase into the cell. However, after infecting the cell and releasing their viral RNA, they depend on precursors necessary for replication of their viral RNA. The virus is dependent on ribose-5-phosphate (R5P) from the host cell as an essential building block for their replication.

The central switch for the regulation of cell cycle and cell proliferation as well as for the sufficient supply of R5P building blocks is provided by transketolase-like 1 (TKTL1) [Li et al., 2019], which therefore represents a good target for antiviral therapy.

Transketolases (TKT) are key enzymes of the pentose-phosphate-pathway (PPP). They form dimers and are activated by the binding of thiamine diphosphate and a divalent cation. Li et al. have shown that during cell cycle TKTL1 is overexpressed in late G1 phase and S phases. This results in the formation of stable TKT/TKTL1-heterodimers which exhibit a different transketolase activity than TKT-homodimers. The formation of TKT/TKTL1 heterodimers shifts glucose metabolism towards R5P formation, resulting in an accumulation of R5P in the cell [Li et al. 2019; Coy JF 2017]. In addition, it has been shown in cancer cells that TKTL1 is involved in the regulation of cell division via a feed-forward loop mechanism, i.e., that the end product of the enzyme reaction further enhances the reaction [Sun W et al. 2010]. In terms of cell division, this binary procedure ("TKTL1 switch on/off"; TKTL1 on = shifts the glucose metabolism towards R5P formation) appears to be judicious: during the S phase, in which DNA duplication occurs in the cell, the DNA is unpackaged and accordingly extremely vulnerable to mutations. It is therefore essential to complete this phase as quickly as possible in order to minimize the risk of DNA damage. Thus, by means of a binary regulatory mechanism, the cell ensures that cell division - once it has begun - can proceed safely and completely and that sufficient building blocks (R5P) are available for DNA synthesis and DNA repair during this phase. These R5P building blocks are also required by RNA viruses for replication and form the basis for the replication of RNA viruses in the cell.

Since transketolases are essential for the formation of R5P and thus for the replication of SARS-CoV-2 in the host cell, they represent an attractive target for drug therapy: Substances that inhibit the activity of the transketolases prevent the accumulation of R5P, the essential building block for virus replication, in the cell. In this way, the virus can be deprived of its essential basis for its replication. Thus, this therapeutic approach, which fundamentally prevents viral replication - unlike a vaccine - is also independent of mutations of the virus.

Thiamine antagonists, such as oxythiamine (OT), are irreversible inhibitors of thiamine-dependent enzymes such as transketolases and efficiently inhibit sugar metabolism [Tylicki et al. 2018]. Since the TKT/TKTL1 heterodimer, which is responsible for enhanced R5P synthesis, is being dependent on thiamine, the use of OT or B-OT enables an inhibition of the TKT/TKTL1 heterodimer thereby reducing the R5P synthesis in a dose dependent manner. Thus, it can be assumed that ribose-5-phosphate can be reduced to a certain critical low level, where virus's replication is significantly slowed down or even no longer possible due to limitation of ribose-5-phosphate concentration in cells as a building block for virus replication.

Recent studies in SARS-CoV-2 infected Caco-2 cell lines [Bojkova D et al. 2020 and 2021] have shown that a) the pentose phosphate pathway was activated after SARS-CoV-2 infection and b) a dose-dependent inhibition of SARS-CoV-2 replication was detectable when non-toxic B-OT concentrations were applied.

